9.4.3.4 Treatment Given for Adverse Event

Any treatment (e.g., medications or procedures) given for the AE should be recorded on the Adverse Event Case Report Form. Treatment should also be recorded on the concomitant treatment or ancillary procedures eCRF, as appropriate.

9.4.3.5 Outcome of the Adverse Event

If the event is a non-serious AE, then the event's outcome is characterized by one of the following:

- **AE Persists:** Patient terminates from the trial and the AE continues
- **Recovered:** Patient recovered completely from the AE
- **Became Serious:** The event became serious (the date that the event became serious should be recorded as the Resolution Date of that AE and the Onset Date of the corresponding SAE)
- **Change in Severity (if applicable):** AE severity changed

If the event is a SAE, then the event's outcome is characterized by one of the following:

- **Ongoing:** SAE continuing
- **Persists (as non-serious AE):** Patient has not fully recovered but the event no longer meets serious criteria and should be captured as an AE on the non-serious AE eCRF (the SAE resolution date should be entered as the date of onset of that AE)
- **Recovered:** Patient recovered completely from the SAE (the date of recovery should be entered as the SAE resolution date)
- **Fatal:** Patient died (the date of death should be entered as the SAE resolution date)

9.5 Procedures for Handling Special Situations

9.5.1 Abnormalities of Laboratory Tests

Clinically-significant abnormal laboratory test results may, in the opinion of the Investigator, constitute or be associated with an AE. Examples of these include abnormal laboratory results that are associated with symptoms, or require treatment, e.g., bleeding due to thrombocytopenia, tetany due to hypocalcemia, or cardiac arrhythmias due to hyperkalemia. Whenever possible, the underlying diagnosis should be listed in preference to abnormal laboratory values as AEs.

Clinically-significant abnormalities will be monitored by the Investigator until the parameter returns to its baseline value or until agreement is reached between the Investigator and Sponsor Medical Monitor (or designee). Laboratory abnormalities deemed not clinically-significant (NCS) by the Investigator, or those associated with hemodialysis or ESRD (e.g., asymptomatic mild to moderate hyperkalemia, hyperphosphatemia, etc.) should not be reported as AEs.

Similarly, laboratory abnormalities reported as AEs by the Investigator should not be deemed NCS on the laboratory sheet.

The Investigator is responsible for reviewing and signing all laboratory reports. The signed clinical laboratory reports will serve as source documents and should include the Investigator's assessment of clinical significance of out of range/abnormal laboratory values.

9.5.2 Prescheduled or Elective Procedures or Routinely Scheduled Treatments

A prescheduled or elective procedure or a routinely scheduled treatment will not be considered a SAE, even if the subject is hospitalized; the Study Center must document all of the following:

- The prescheduled or elective procedure or routinely scheduled treatment was scheduled (or was on a waiting list to be scheduled) prior to obtaining the subject's consent to participate in the study
- The condition that required the prescheduled or elective procedure or routinely scheduled treatment was present before and did not worsen or progress in the opinion of the Investigator between the subject's consent to participate in the study and the timing of the procedure or treatment
- The prescheduled or elective procedure or routinely scheduled treatment is the sole reason for the intervention or hospital admission

9.5.3 Dosing Errors

Study Drug (ISIS 416858 or placebo) errors should be documented as Protocol Deviations. A brief description should be provided in the deviation, including whether the subject was symptomatic (list symptoms) or asymptomatic, and the event accidental or intentional.

Dosing details should be captured on the Dosing Case Report Form. If the subject takes a dose of Study Drug (ISIS 416858 or placebo) that exceeds protocol specifications and the subject is symptomatic, then the symptom(s) should be documented as an AE and be reported per [Section 9.4](#).

Should an overdose occur, the Investigator or designee should refer to the Guidance to Investigator's section of the Investigator's Brochure and contact the Sponsor or designee within 24 hours.

9.5.4 Contraception and Pregnancy

Subjects must continue to use appropriate highly effective contraception with their partners, or refrain from sexual activity, as described in [Section 6.3.1](#).

If a subject becomes pregnant or a pregnancy is suspected, or if a male subject makes or believes that he has made someone pregnant during the study, then the Study Center staff must be informed immediately. An Initial Pregnancy Form should be submitted to the Sponsor or designee **within 24 hours** of first learning of the occurrence of pregnancy. Follow-up information including delivery or termination is reported by designating as 'Follow-up' on the Pregnancy Forms and reported within 24 hours.

Payment for all aspects of obstetrical care, child or related care will be the subject's responsibility.

Female subjects: If a suspected pregnancy occurs while on the study (including follow-up), a pregnancy test will be performed. The subject with a confirmed pregnancy will be immediately withdrawn from treatment with Study Drug. However, the subject will be encouraged to complete the post-treatment follow-up portion of the study to the extent that study procedures do not interfere with the pregnancy. Regardless of continued study participation, the study physician will assist the subject in getting obstetrical care and the progress of the pregnancy will be followed until the outcome of the pregnancy is known (i.e., delivery, elective termination, or spontaneous abortion). If the pregnancy results in the birth of a child, the Study Center and Sponsor may require access to the mother and infant's medical records to obtain additional information relevant to the pregnancy outcome. Follow-up will be performed to the extent permitted by the applicable regulations and privacy considerations; e.g., pregnancy ICF may be required.

Male subjects: The progress of the pregnancy of a male subject's partner should be followed until the outcome of the pregnancy is known (i.e., delivery, elective termination, or spontaneous abortion). If the pregnancy results in the birth of a child, **the Study Center and Sponsor may follow-up with the mother and may request access to the mother and infant's medical records to obtain additional information relevant to the pregnancy and the newborn child.** Follow-up will be performed to the extent permitted by the applicable regulations and privacy considerations, e.g., partner ICF may be required.

10. STATISTICAL CONSIDERATIONS

10.1 Study Endpoints, Subsets, and Covariates

10.1.1 Safety and Tolerability

The primary safety outcome is the combination of MB and CRNMB during the treatment period (or early study termination). For the subgroup of subjects evaluated for platelet function and/or activation, an analysis of pre- and post-treatment results with ISIS 416858 may be conducted and compared to treatment with placebo.

The safety and tolerability of ISIS 416858 will be assessed by determining the incidence and severity of AEs and will be evaluated by reviewing:

- AEs (including bleeding events)
- Vital signs and weight
- Physical examination
- Clinical laboratory tests
- Coagulation parameters
- Use of concomitant medications

10.1.2 *Pharmacodynamic Outcomes*

- Change from Baseline in FXI antigen and activity
- Change from Baseline in aPTT
- The extent and frequency of clotting on the dialysis filters and circuit

10.1.3 *Exploratory Outcomes*

- Incidence of myocardial infarction (MI), stroke, systemic embolism, and cardiovascular (CV) mortality

10.1.4 *Other Study Outcomes and Evaluations*

- Urea Reduction Ratio
- PK

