1.3.5 Platelet Function Testing

For the subgroup of subjects evaluated for platelet function and/or activation, an analysis of pre- and post-treatment results with ISIS 416858 may be conducted overtime and compared to treatment with placebo

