All subjects who are randomized without missing more than 2 doses during the first 12 weeks or more than 5 doses over the 26-week Treatment Period and who do not have any major protocol violations that would affect the interpretation or integrity of the study results.

Safety Population:

All subjects randomized who have received at least 1 dose of Study Drug. Results for Cohorts A and B will be summarized under the treatment to which patients received.

Atrial Fibrillation (AF) Substudy population:

All randomized subjects who were reported at baseline as having a documented history of atrial fibrillation and have received at least 1 dose of Study Drug (ISIS 416858 or placebo).

PK Substudy Population:

All randomized subjects who participated in the PK subgroup and have received at least 1 dose of active Study Drug (ISIS 416858) and had at least 1 PK sample collected and analyzed with evaluable results for ISIS 416858 concentration.

PK Population:

All randomized subjects who have received at least 1 dose of active Study Drug (ISIS 416858) and had at least 1 PK sample collected and analyzed with evaluable results for ISIS 416858 concentration.

Platelet Function/Activation Substudy Population:

All subjects who participated in the Platelets Function/Activation substudy by having at least 1 evaluable sample assessed for flow cytometry and have received at least 1 dose of active Study Drug (ISIS 416858 or placebo).

In addition to the above analysis populations, it is recognized that some data displays will be provided for "All Screened" and "Screening Failures" patients.

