A confirmed laboratory value is based on consecutive lab values within 7 days. If that value is in the same or worse category, then the initial value is confirmed. If the consecutive value is in a better category, then the initial value is confirmed using consecutive value category. If there is no retest within 7 days, the initial value is presumed confirmed. If there are multiple results on the same day (no matter from the same lab vendor or different lab vendors), then the worst value will be utilized in the analysis.

BCH flow cytometry data for platelet function will be summarized separately. The Versiti (Blood Centers of Wisconsin) data will be listed.

All patients meeting safety monitoring and stopping rules will be listed.

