2.6 Other Study Outcomes and Evaluations

Blood Urea Nitrogen (BUN) will be used for Urea Reduction Ratio (URR) analysis in the Safety population.

$$\text{URR} = (\text{Upre} - \text{Upost}) / \text{Upre} \times 100\%$$

where U_{pre} is the pre-dialysis blood urea nitrogen (BUN) level in serum and U_{pos1} is the post-dialysis blood urea nitrogen (BUN) level in serum. The URR generated from Lab will be used.

URR and sp Kt/v values as well as the change and percent change from baseline will be summarized for each visit by treatment group for the safety population. Single pool dialyzer clearance of urea (sp Kt/v) from CRF will be used in the summary.

Change and percent change from baseline will be compared between each of the ISIS 416858-treated groups and the pooled placebo group using the ANOVA or Wilcoxon Rank Sum test, as appropriate. The normality will be tested by applying Kolmogorov-Smirnov test on the residuals (difference between individual values and group mean).

Changes in dialysis prescription will be listed.

2.6.J Platelet Function tests

All Flow cytometry and PFA results will be summarized by visit and treatment for Platelet Function/Activation Substudy population.

Flow cytometry results (and potentially a report with interpretation of the results) will be provided directly by Boston Children's hospital. Flow cytometry results of platelet-monocyte and platelet-neutrophil aggregates and platelet surface P-selectin and platelet surface activated GPIIb-IIa will be compared between each of the ISIS 416858-treated groups and the pooled placebo group.

The PFA results of duplicate closure times for each evaluated cartridges of collagen/EPI, collagen/ADP, and INNOVANCE PFA®P2Y (optional cartridge) for change and percent change from baseline will be compared between each of the ISIS 416858-treated groups and the pooled placebo group for subjects that have the PFA tests performed.

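### The SAP admits subjects to the platelet substudy population only through a flow cytometry sample, then tabulates all PFA results in that population

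*Combined protocol and SAP*

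**What the plan says.** Protocol 3.1.1 and 10.1.1 describe a subgroup of about 12 subjects per cohort tested for platelet function, activation or both. Protocol 10.1.1 puts it this way: "For the subgroup of subjects evaluated for platelet function and/or activation, an analysis of pre- and post-treatment results" may be conducted. SAP 1.3.5 repeats this: "For the subgroup of subjects evaluated for platelet function and/or activation, an analysis of pre- and post-treatment results with ISIS 416858 may be conducted".

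SAP 2.1.2 defines the Platelet Function/Activation Substudy Population. A subject enters by having "at least 1 evaluable sample assessed for flow cytometry" and by having received "at least 1 dose of active Study Drug (ISIS 416858 or placebo"). A PFA result gives no route in.

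SAP 2.6.1 then makes two statements about PFA:

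- Summaries: "All Flow cytometry and PFA results will be summarized by visit and treatment for Platelet Function/Activation Substudy population".
- Comparison: change and percent change in closure times are compared between each dose group and "the pooled placebo group for subjects that have the PFA tests performed".

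SAP 2.3.4 adds: "BCH flow cytometry data for platelet function will be summarized separately".

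**The concern.** Two assays are reported, and the evaluability of one decides who appears in the summary tables of the other. They are separate tests: SAP 2.6.1 has the flow cytometry results supplied directly by an outside hospital laboratory, while PFA is a cartridge closure-time test. Nothing about a failed flow sample makes a closure time invalid, so there is no reason for the PFA summaries to depend on it.

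Protocol 10.1.1 mentions the platelet analysis under safety and tolerability, and the substudy is small, so a needless exclusion costs scarce data. There is also a consistency problem. If the by-visit PFA table uses the substudy population and the PFA comparison uses everyone with PFA performed, the descriptive statistics and the test beside them may describe different subjects. The SAP would not tell a programmer which set was meant.

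**Working it through.** The plan gives no sample size, power or precision figure for the substudy, so there is no figure to reproduce. The check is a comparison of texts, followed by a small calculation of scale.

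**Step 1. Who is in each set?** Take four dosed subjects in the subgroup.

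| Evaluable flow sample | PFA result | In protocol subgroup (3.1.1, 10.1.1) | In SAP 2.1.2 population | In PFA summary (2.6.1) | In PFA comparison (2.6.1) |
|---|---|---|---|---|---|
| Yes | Yes | Yes | Yes | Yes | Yes |
| Yes | No | Yes | Yes | No PFA data | No |
| No | Yes | Yes | **No** | **No** | **Unclear** |
| No | No | No data | No | No | No |

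Only the third row is a problem. Exclusion from the summary follows directly from SAP 2.1.2 and 2.6.1 read together. Exclusion from the comparison depends on whether the closing phrase of SAP 2.6.1 restricts the substudy population or stands in its place, and both readings fit the sentence.

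**Step 2. Group sizes.** Inputs: about 12 subjects per cohort (protocol 3.1.1), 3:1 allocation within each cohort (protocol 3.1), three cohorts, and placebo pooled across cohorts (SAP 2.1.1).

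- Active per dose: 12 × 3/4 = 9
- Pooled placebo: 3 × 12 × 1/4 = 9
- One subject as a share of a group: 1/9 = 11%

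**Step 3. Illustration of precision.** The documents do not give the number of subjects in the third row. Assume k are lost from a dose group and m from pooled placebo, each from 0 to 3. With a common variance, the standard error of a dose-versus-placebo difference changes by the factor

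√(1/(9−k) + 1/(9−m)) / √(1/9 + 1/9)

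| k | m | Factor |
|---|---|---|
| 0 | 0 | 1.00 |
| 1 | 0 | 1.03 |
| 1 | 1 | 1.06 |
| 2 | 2 | 1.13 |
| 3 | 3 | 1.22 |

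The increase therefore runs from 0% to 22% over the assumed range. It applies to the comparison only on the restrictive reading.

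**Step 4. The dosing clause.** The two PK populations in SAP 2.1.2 use the term for active drug followed by ISIS 416858 alone. The platelet definition uses the same term, but its parenthesis names ISIS 416858 or placebo. The adjective and the parenthesis disagree.

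**The case against.** The strongest reply is that the affected subject is hard to produce. One evaluable flow sample at any visit is enough for entry, and platelet testing is scheduled at Weeks 1, 12, 26 and 38. A change in closure time needs a baseline and a later value, so a subject contributing to the PFA comparison attended at least two platelet visits. All of that subject's flow samples would have to be missing or unevaluable. Appendix A has a single combined row for platelet testing and shows no PFA-only path. The phrase about subjects who had PFA performed suggests, if anything, that PFA is the less complete assay. All of this stands, and it limits the likely size to little or nothing. It does not remove the rule as written.

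A reader might also infer more than the documents support:

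- **That subjects with PFA only are dropped from the whole function analysis.** This is established for the summary tables only. The comparison sentence names its own set.
- **That flow cytometry is the activation test and PFA the function test.** SAP 2.3.4 calls the flow data platelet function data. The point needs only two assays with one of them controlling entry.
- **That the population contains no placebo subjects.** The parenthesis includes placebo, the glossary defines Study Drug as either, and SAP 2.6.1 compares with pooled placebo. The word is a drafting slip.
- **That the PFA comparison is biased.** Nothing in the documents links flow failure to closure times or to treatment. If they are unrelated, the cost is precision only.

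The analysis is also optional in protocol 10.1.1 and SAP 1.3.5, and SAP 2.6 places it among other outcomes.

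**Conclusion.** The point holds in a narrow form. SAP 2.1.2 and 2.6.1 together exclude from the PFA summary tables any dosed subject with valid PFA results but no evaluable flow sample, although the protocol's subgroup would include that subject. Whether the PFA comparison excludes the same subject is undetermined, so the two could use different sets.

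The number affected is unknown and may be zero. The 11% per lost subject assumes that the substudy recruits to plan and keeps the 3:1 ratio. The percentages in Step 3 rest on assumed losses and do not measure a demonstrated loss. The error lies in SAP 2.1.2 and 2.6.1; protocol 10.1.1 is the text against which they are compared and needs no change. This is a minor correction, worth making because the better rule costs almost nothing.

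**What to change.** In SAP 2.1.2, define the Platelet Function/Activation Substudy Population as subjects in the substudy with at least one evaluable flow cytometry or PFA result who received at least one dose of Study Drug (ISIS 416858 or placebo). Delete the word active.

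In SAP 2.6.1, state that each assay is both summarized and compared in all members of that population with an evaluable result for that assay. For change from baseline, this means an evaluable baseline and post-baseline result. This settles which set the PFA comparison uses.

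The cost is an edit to each of the two SAP sections, with no new data or procedures. Denominators will differ between the flow and PFA tables, so each table should show its own number of subjects.

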10.2 Sample Size Considerations

The sample size was selected based on prior experience to ensure that the safety, tolerability and PK/PD relationships will be adequately assessed while minimizing unnecessary patient exposure. There is no statistical rationale for the selected sample size.

10.3 Populations

Intent to Treat Population: All subjects randomized who have received at least 1 dose of Study Drng.

Per Protocol Population: All subjects who are randomized without missing more than 2 doses during the first 12 weeks or more than 5 doses over the 26-week Treatment Period and who do not have any major protocol violations that would affect the interpretation or integrity of the study results.

Safety Population: All subjects randomized who have received at least 1 dose of Study Drng.

PK Population: All subjects who have received at least 1 dose of active Study Drng (ISIS 416858), and have at least 1 PK sample collected and analyzed with evaluable results.

10.4 Definition of Baseline

Baseline for the routine clinical assessments of chemist:ly and hematology, PD markers, assessment of clotting, PK assessments, vital signs and ECG for the study will be the last non-missing value prior to the first administration of Study Drug (ISIS 416858 or placebo) and prior to dialysis on Day 1 ([Appendix A](#)). If Day 1 values are not available, screening values will be used. For Urea Reduction Ratio, the BUN blood collections prior to dialysis as well as the post-dialysis sample on Day 1 will be used to establish baseline.

10.5 Interim Analysis

No interim analysis is planned. However, dming the study, an unblinded interim analysis may be conducted to assess the safety, PK/PD, and exploratory efficacy of the results. The analysis will be executed with controlled dissemination to ensme the integrity of ongoing data collection

while maintaining sufficient blinding in the study. Details of these controls will be described in the SAP.

10.6 Planned Methods of Analysis

Descriptive summary analysis including mean, median, standard deviation, interquartile range (25th percentile, 75th percentile), and range (minimum, maximum) for continuous variables, and counts and percentages for categorical variables will be used to summarize most data.

Safety and PD assessments will be performed on the Safety population. Exploratory efficacy and clotting assessment measures may be assessed on the Per Protocol population.

10.6.1 Demographic and Baseline Characteristics

Demographic and Baseline characteristics will be summarized using descriptive statistics by treatment group. Subject randomization will be summarized by treatment group. The subject disposition will be summarized. All subjects emolled will be included in a summary of subject disposition.

10.6.2 Safety Analysis

Treatment duration and amount of Study Drng (ISIS 416858 or placebo) received will be summarized by treatment group. Subject incidence rates of all AEs will be tabulated by the Medical Dictionary for Regulatory Activities (MedDRA™) system organ class, and by MedDRA™ term. Tables and/or narratives of treatment-emergent deaths, serious and significant AEs, including early withdrawals due to AEs, will also be provided.

All treatment-emergent AEs, all treatment-emergent AEs potentially related to Study Drng, all treatment-emergent serious AEs, and all treatment-emergent serious AEs potentially related to Study Drng (ISIS 416858 or placebo) will be summarized.

Laboratory tests to ensure subject safety including chemistly panel, complete blood count with differential, coagulation panel, complement etc., will be summarized by study visits for each treatment group. These safety variables will also be presented as change and percent change from Baseline over time after Study Drng (ISIS 416858 or placebo) administration, as appropriate.

Vital sign and ECG measures will be tabulated by treatment group. In addition, the number of subjects who experience abnormalities in clinical laboratory evaluations will be summarized by treatment group.

Incidence of bleeding events including the following will be tabulated by treatment:

- MB
- CRNMB
- Minor bleeding
- Combination of MB and CRNMB

Physical examination data will be provided in the data listing. Concomitant medications will be coded using World Health Organization (WHO) Drng dictionruy and summarized by treatment, ATC class and generic name.

